## TITLE COLLAPSIBLE PESSARY FEASIBILITY TRIAL STATISTICAL ANALYSIS PLAN

- 13.5.2 Mean difference (current pessary – study pessary) in number of self-management events per month will be reported.
- 13.5.3 The number of self-managers with the current pessary and study pessary will be reported.
- 13.5.4 We will use a two-tailed t-test to test the null hypothesis that the mean difference score between baseline (current pessary) and study pessary in the frequency of self-management is zero. This test is equivalent to a matched samples t-test. The p-value will be reported.
- 13.5.5 We will use a two-tailed t-test to test the null hypothesis that the mean difference score between baseline (current pessary) and study pessary in the number of self-managers is zero. This test is equivalent to a matched samples t-test. The p-value will be reported.

## TITLE COLLAPSIBLE PESSARY FEASIBILITY TRIAL STATISTICAL ANALYSIS PLAN

**14.0 EASE OF INSERTION & REMOVAL (SECONDARY)**

- 14.1 Endpoint
  - 14.1.1 Ease of insertion of study pessary compared to current pessary for self-managers
  - 14.1.2 Ease of removal of study pessary compared to current pessary for self-managers
  - 14.1.3 Ease of insertion of study pessary by subject for self-managers
  - 14.1.4 Ease of removal of study pessary by subject for self-managers
- 14.2 Data collection method
  - 14.2.1 Ease will be assessed using a Visual Analog Scale (VAS) with a 10 cm linear continuum in which 0 represents very easy and 10 represents very difficult.
- 14.3 Analysis group
  - 14.3.1 At most, for each subject two VAS ease of use scores will be collected for each of insertion of current pessary, removal of the current pessary, insertion of the study pessary, and removal of the study pessary. Subject's VAS ease of use scores will be included in the comparative analysis group if the subject has at least 1 data point for both the study pessary and their current pessary and in the non-comparative analysis group if they have at least 1 data point for the study pessary.
- 14.4 Data analysis plan
  - 14.4.1 For each subject, average ease of use scores for the current pessary and study pessary will be calculated.
  - 14.4.2 For each subject, a difference (current pessary – study pessary) in average ease of use scores will be calculated.
- 14.5 Reportable outcomes
  - 14.5.1 Average and standard deviation of the ease of current and study pessary insertion and removal will be reported.
  - 14.5.2 We will use a two-tailed t-test to test the null hypothesis that the mean difference score between baseline (current pessary) and study pessary in the ease of insertion is zero. This test is equivalent to a matched samples t-test. The p-value will be reported.
  - 14.5.3 We will use a two-tailed t-test to test the null hypothesis that the mean difference score between baseline (current pessary) and study pessary in the ease of removal is zero. This test is equivalent to a matched samples t-test. The p-value will be reported.

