Other	Ease of insertion of study pessary by subject for self-managers	Post treatment [Week 16]	Ease will be assessed using a Visual Analog Scale (VAS) with a 10cm linear continuum in which 0 represents most difficulty and 10 represents most ease.
Other	Ease of removal of study pessary by subject for self-managers	Post treatment [Week 16]	Ease will be assessed using a Visual Analog Scale (VAS) with a 10cm linear continuum in which 0 represents most difficulty and 10 represents most ease.

5.0 Study Intervention/Investigational Agent Please see attached document for device description and non-significant risk rationale.

THE COLLAPSIDEL PESSANTI LASIDILITI TRIAL PROTOCO

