Visit 1 [research purposes] will aim to be scheduled between 3 and 5 weeks from Visit 0 (the conclusion of the washout period). Demographic and historical data will be extracted from the Electronic Medical Record (EMR) if not completed at Visit 0 and supplemented by the subject as needed. Global subject satisfaction of the current pessary will be assessed using a Visual Analog Scale (VAS) with a 10 cm linear continuum in which 0 represents no satisfaction and 10 represents complete satisfaction. As in Visit 0, the current pessary will be observed in situ for the presence of rotation and its ability to support prolapse by measuring the distance of the most dependent compartment of the subject's prolapse to the hymen (points Ba and Bp), as well as the distance from the leading edge of the current pessary to the hymen. The current pessary will be removed, washed, placed in a sealed bag, labeled and either stored or given to the subject for them to return with at their final visit. The physical exam will be repeated as in Visit 0, and the presence of perineal disruption associated current pessary removal will be noted. The appropriate study pessary size for the subject based on the provided mapping from the subject's current pessary and practitioner's expertise will be selected at random from the inventory of study pessaries, removed from its sealed bag, and the study pessary's serial number (labeled on the bag) will be recorded. The subject will be fit with the study pessary. If a study pessary cannot be fit, and the patient is willing, they can be fit with a different sized pessary at Visit 1 or can remain in the study and return for a second attempt to be fit with a study pessary at Visit 2. A VAS will be used to assess the perceived discomfort with removal of the current pessary and, separately, with insertion of the study pessary. For self-managers, ease of current pessary removal and reinsertion will be noted using a VAS and teaching will be provided on the proper technique to insert and remove the study pessary.

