Visit 3 [research purposes] will occur at the conclusion of the 3-month (from Visit 1) treatment phase - a typical length of time between routine visits for patients who choose long term pessary management of their prolapse. It can be scheduled in a window between 11 and 13 weeks from Visit 1. When the subject returns for Visit 3, a physical exam will be repeated, as in previous visits, for comparative data. The study pessary will be observed in situ for the presence of rotation and its ability to support prolapse by measuring the distance of the most dependent compartment of the subject's prolapse to the hymen (Points Ba and Bp), as well as the distance from the leading edge of the study pessary to the hymen. A VAS will be used to assess discomfort with removal of the study pessary, discomfort with reinsertion of their current pessary, and their global satisfaction of the study pessary. The subject will have been instructed to return with their current pessary which was removed in Visit 1. If the subject's current pessary is not brought to the visit, they will be given a new pessary of the size and style of their current pessary. Each subject will complete the PFDI-20, PFIQ-7, and PISQ-R for a post treatment comparison. For self-managers, other data collected will include frequency of removal and a VAS for ease of study pessary insertion and removal.

Additional Visits: Subjects will be seen as necessary and adverse events will be managed according to standard of care. If the study pessary falls out after Visit 1, the subject may be seen at their convenience for reinsertion or resizing. If a study pessary cannot be fit and retained, the subject will be withdrawn from the study and their current pessary will be placed. If the subject's current pessary is not brought to the visit, they will be given a new pessary of the size and style of their current pessary.

Special Circumstances: If a subject dies between Visit 1 and Visit 3, an attempt will be made to contact the coroner to retrieve the study pessary. If the study pessary cannot be retrieved, a copy of the death certificate will be obtained.

The study pessary is the only device that will be used in this trial. There will be no placebo devices placed. The study pessary is not cleared by the FDA, and a rationale is provided for a non-significant risk device claim in the attached documents.

Data Collected

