## TITLE COLLAPSIBLE PESSARY FEASIBILITY TRIAL STATISTICAL ANALYSIS PLAN

**10.0 GLOBAL SATISFACTION (SECONDARY)**

- 10.1 Endpoint
  - 10.1.1 Global assessment of study pessary satisfaction compared to current pessary
  - 10.1.2 Global assessment of study pessary satisfaction
- 10.2 Data collection method
  - 10.2.1 Satisfaction will be assessed using a Visual Analog Scale (VAS) with a 10 cm linear continuum in which 0 represents no satisfaction and 10 represents complete satisfaction.
- 10.3 Analysis group
  - 10.3.1 Global satisfaction is recorded at visit 1 for the current pessary and visit 3 for the study pessary, so only subjects who complete data collections forms through visit 3, or provide a score for both the current and study pessary before exiting the study, will be included in the analysis.
- 10.4 Data analysis plan
  - 10.4.1 For each subject, a difference (current pessary – study pessary) in satisfaction scores will be calculated.
- 10.5 Reportable outcomes
  - 10.5.1 Average and standard deviation of the global satisfaction of current and study pessary will be reported.
  - 10.5.2 Mean difference (current pessary – study pessary) in satisfaction scores will be reported.
  - 10.5.3 We will use a two-tailed t-test to test the null hypothesis that the mean difference score between baseline (current pessary) and study pessary for global satisfaction is zero. This test is equivalent to a matched samples t-test. The p-value will be reported.
  - 10.5.4 Cundiff et al. dichotomized VAS scores for pessary satisfaction into high satisfaction (greater than or equal to 80 mm) and low satisfaction (less than 80 mm). For this study, we similarly deemed a VAS of 80 mm would indicate high satisfaction. We will use a one-sided t-test to test the null hypothesis that the mean global satisfaction score for the study pessary is less than 80 mm. The p-value will be reported.

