## TITLE COLLAPSIBLE PESSARY FEASIBILITY TRIAL STATISTICAL ANALYSIS PLAN

**11.0 PAIN ASSOCIATED WITH INSERTION & REMOVAL (SECONDARY)**

- 11.1 Endpoint
  - 11.1.1 Pain associated with study pessary insertion compared to current pessary
  - 11.1.2 Pain associated with study pessary removal compared to current pessary
- 11.2 Data collection method
  - 11.2.1 Pain will be assessed using a VAS with a 10 cm linear continuum in which 0 represents no pain and 10 represents worst pain.
- 11.3 Analysis group
  - 11.3.1 At most, for each subject two VAS pain scores will be collected for each of insertion of current pessary, insertion of the study pessary, removal of the current pessary, removal of the study pessary. Subject's VAS pain scores will be included in the comparative analysis group if the subject has at least 1 data point for both the study pessary and their current pessary and in the non-comparative analysis group if they have at least 1 data point for the study pessary.
- 11.4 Data analysis plan
  - 11.4.1 For each subject, average pain scores for the current pessary and study pessary will be calculated.
  - 11.4.2 For each subject, a difference (current pessary – study pessary) in average pain scores will be calculated.
- 11.5 Reportable outcomes
  - 11.5.1 Average and standard deviation of the pain of current and study pessary insertion and removal will be reported.
  - 11.5.2 We will use a two-tailed t-test to test the null hypothesis that the mean difference score between baseline (current pessary) and study pessary for pain during insertion is zero. This test is equivalent to a matched samples t-test. The p-value will be reported.
  - 11.5.3 We will use a two-tailed t-test to test the null hypothesis that the mean difference score between baseline (current pessary) and study pessary for pain during removal is zero. The p-value will be reported.

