## TITLE COLLAPSIBLE PESSARY FEASIBILITY TRIAL STATISTICAL ANALYSIS PLAN

## 15.0 TEST REPORT

- 15.1 The data will be collected according to CP-002-01 Collapsible Pessary Feasibility Trial Protocol and the CP-002-03 Collapsible Pessary Feasibility Trial Data Collection Form and analyzed according to the procedure described above. Results of the analysis shall be documented in a written test report, as described in SOP-1003 Design Control. F-3006 Test Report Template may be used.
- 15.2 Deviations from the procedure will be reviewed for impact, approved by the project team and documented in the test report.

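### The protocol and the SAP anchor the ease-of-insertion and ease-of-removal VAS in opposite directions, so the ease results could be reported the wrong way round

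*SAP*

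**What the plan says.** Protocol 4.0 has two rows for ease in self-managers, one for insertion and one for removal. Both concern the study pessary at Week 16, both are classed as Other, and both use a 10 cm VAS "in which 0 represents most difficulty and 10 represents most ease". A high score is good.

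SAP 14.2.1 covers the same measurements with a 10 cm VAS "in which 0 represents very easy and 10 represents very difficult". A high score is bad. SAP section 14 classes ease as secondary and has four endpoints: study against current pessary for insertion (14.1.1) and removal (14.1.2), and the study pessary alone for insertion (14.1.3) and removal (14.1.4). Under 14.4.2, "a difference (current pessary – study pessary) in average ease of use scores will be calculated". Section 14.5 reports means and SDs for each pessary and p-values from two-tailed paired t-tests.

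On collection, Protocol 6.0 says of Visit 1 that "ease of current pessary removal and reinsertion will be noted using a VAS", and at Visit 3 it lists "a VAS for ease of study pessary insertion and removal". Neither gives anchors. SAP 15.1 states: "The data will be collected according to CP-002-01 Collapsible Pessary Feasibility Trial Protocol and the CP-002-03 Collapsible Pessary Feasibility Trial Data Collection Form".

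**The concern.** One scale has two opposite definitions, and each sits in a document with a claim to govern it: the protocol governs collection and the SAP governs analysis. If scores are gathered on the protocol's anchors and read by the SAP's, the pessary that subjects found easier would be reported as the harder one. The two study-pessary means would be misread in the same way.

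This matters for this device. Protocol 3.0 names difficulty of self-removal and self-insertion as the main failing of current pessaries and hypothesises that the study pessary is simpler to use. Subjects' ability to insert and remove it is a listed objective in Protocol 1.0. A reversed ease result would misstate the evidence on that point.

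**Working it through.** The plan gives no sample size, power or expected value for ease, so there is no figure to reproduce. The check has three parts.

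**1. Can the direction be settled from the documents?**

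| Source | What it gives |
|---|---|
| Protocol 4.0, both ease rows | high = easy |
| SAP 14.2.1 | high = difficult |
| Protocol 6.0, Visits 1 and 3 | VAS named, no anchors |
| SAP 15.1 | defers to both the protocol and form CP-002-03 |
| SAP 16.0 revision history | no change of ease anchors recorded |
| SAP section 14 | no recoding step |

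The other VAS sections supply no convention. Satisfaction (SAP 10.2.1) is scored so that "0 represents no satisfaction and 10 represents complete satisfaction"; with current minus study, a negative difference favours the study pessary. Pain (SAP 11.2.1) is scored so that "0 represents no pain and 10 represents worst pain"; with the same subtraction, a positive difference favours it. Ease behaves like satisfaction under the protocol anchors and like pain under the SAP anchors. The documents therefore leave the direction open.

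**2. Effect on the comparative endpoints (14.1.1, 14.1.2)**

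Reversing the scale replaces each score x by 10 − x. The difference becomes (10 − current) − (10 − study) = −(current − study). The mean difference and t change sign. The SD of the differences, |t| and the two-sided p-value do not change.

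Illustration, with assumed protocol-scale means of 5 (current) and 8 (study, so easier):

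- Protocol anchors: 5 − 8 = −3 cm. Read by the SAP anchors, this says the study pessary is 3 cm harder.
- Correctly recoded to the SAP anchors: means of 10 − 5 = 5 and 10 − 8 = 2, so 5 − 2 = +3 cm, the study pessary being easier.

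With t = difference / (SD/√n), and n and the paired SD also assumed:

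| n | SD (cm) | \|t\| | two-sided p, either coding |
|---|---|---|---|
| 12 | 4 | 3/(4/√12) = 2.60 | 0.025 |
| 20 | 3 | 3/(3/√20) = 4.47 | 0.00026 |
| 25 | 2 | 3/(2/√25) = 7.50 | 9.7 × 10⁻⁸ |

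A clearly significant result would look the same whichever pessary it favoured.

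**3. Effect on the study-pessary means (14.1.3, 14.1.4)**

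A mean m read on the wrong anchors stands for 10 − m on the right ones. The misreading is |m − (10 − m)| = |2m − 10|:

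| m (cm) | 5 | 6 | 7 | 8 | 9 |
|---|---|---|---|---|---|
| misreading (cm) | 0 | 2 | 4 | 6 | 8 |

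It vanishes only at the midpoint and grows as the result becomes more decisive.

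**The case against.** The contradiction itself is hard to dispute. The case on the other side is about scope and weight.

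- **The harm depends on a form not available here.** Subjects mark whatever CP-002-03 prints. A wrong result requires the form to carry the protocol anchors and the analyst to rely on SAP 14.2.1 without looking at the form. This stands, and the conclusion is conditional on it. It does not clear the documents, because one of the two anchor statements is wrong whatever the form says.
- **The protocol's anchors cover only the study pessary at Week 16.** This also stands: the direct conflict is with 14.1.3 and 14.1.4. The effect on 14.1.1 and 14.1.2 is an inference, but a short one, since the SAP puts both pessaries on one scale and subtracts.
- **The favourable sign follows once the anchors are settled, and sections 10 and 11 do not state it either.** True. The missing sign statement is not a separate error; it removes a cross-check that would have exposed the conflict.
- **Section 14.5 is not alone in omitting the mean difference.** Sections 9.5.2, 10.5.2 and 13.5.2 list it, but 8.5 and 11.5 also leave it out. The omission is therefore not peculiar to ease. It does mean that the reader takes direction from the two means and their anchors.
- **The numbers are assumed.** They are, and they do not estimate the effect in this trial. The change of sign with an unchanged p-value holds for any data.
- **The endpoints are minor.** They apply to self-managers only and carry no success criterion, which limits the weight of the point.

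**Conclusion.** The concern holds. Protocol 4.0 and SAP 14.2.1 define the same VAS in opposite directions, and nothing in the two documents resolves it.

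If CP-002-03 prints the protocol anchors and the results are read by the SAP, the sign of both comparative ease results reverses and the study-pessary means are misread by |2m − 10| cm, for example 6 cm at an assumed mean of 8. If the form prints the SAP anchors, the analysis reads correctly and the error is confined to the protocol table. Extending the effect to the comparative endpoints assumes that current-pessary ease is collected on the same scale as study-pessary ease, as the SAP implies.

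Type I error, the primary endpoints and the success criteria are unaffected. The point should be fixed because the failure would be silent and bears on a stated objective of the study.

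**What to change.** Before analysis:

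1. Check the ease anchors printed on CP-002-03, for both pessaries and in every form version used.
2. Correct whichever of Protocol 4.0 and SAP 14.2.1 disagrees with the form.
3. Add a sentence to SAP 14.4.2 saying which sign of current minus study means the study pessary is easier.
4. Print the anchors beside the means reported under SAP 14.5.1.
5. Recode as 10 − score only if form versions prove to differ in direction, and record this in the test report. The recoding is approximate, because the two sets of end labels differ in strength as well as direction.

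The cost is one look at the form, a one-line correction and one added sentence. No new data are needed.

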## TITLE COLLAPSIBLE PESSARY FEASIBILITY TRIAL STATISTICAL ANALYSIS PLAN

## 15.0 TEST REPORT

- 15.1 The data will be collected according to CP-002-01 Collapsible Pessary Feasibility Trial Protocol and the CP-002-03 Collapsible Pessary Feasibility Trial Data Collection Form and analyzed according to the procedure described above. Results of the analysis shall be documented in a written test report, as described in SOP-1003 Design Control. F-3006 Test Report Template may be used.
- 15.2 Deviations from the procedure will be reviewed for impact, approved by the project team and documented in the test report.

## 16.0 REVISION HISTORY

Revision	Summary of Changes/Affected Sections
01	Initial release of document
02	Updated to include mean differences described in data analysis plans in reportable outcomes; clarification provided on some analysis group populations

\* Printed copies are uncontrolled unless otherwise identified \*

Before using this document, consult Grand Avenue to confirm current version before use.

CONFIDENTIAL

